2 OBJECTIVES

2.1 Background

Objective of this trial is to assess safety and effectiveness of ExAblate MRgFUS in the treatment of intermediate risk, localized (organ confined) prostate lesions. Investigators selected for the study will be trained on proper use of the ExAblate system (**Appendix B**).

ExAblate treatment will be implemented as a focal lesion-selective therapy, directed at pre-defined volume(s)/sector(s) in the prostate, identified abnormal by mapping biopsy and multi-parametric MRI), rather than a whole gland or hemi-ablation treatment.

Safety: evaluate incidence and severity of adverse events associated with ExAblate's MRgFUS focal treatment of intermediate risk organ confined prostate lesions. The risk of ExAblate treatment-related incontinence and impotence will also be assessed in this study.

Focal MR-Guided Focused Ultrasound Surgery of Intermediate risk, Localized Prostate Lesions

Effectiveness: determine the lesion control effect of ExAblate's MRgFUS focal treatment of intermediate risk organ-confined prostate lesion (confirmed by IMAGE-guided mapping biopsy results).

The proposed study is to evaluate the preliminary effectiveness and safety of the ExAblate 2100 Prostate System for focal treatment of patients with intermediate risk, localized prostate lesions. Study results will be submitted to FDA as previous discussions with the Agency in a 510k for commercial clearance.

Per FDA requirement, the full 510K submission will be performed following the last treated subject completing their 12-Months visit. Assessments of primary efficacy endpoints will compare the 6-months after ExAblate treatment to Baseline measurements. Safety of ExAblate Prostate treatment will be collected for one year after ExAblate.

It should be noted that all patients will be consented and followed up all the way to 24-Months post treatment.

This study will allow any IMAGE-guided biopsy methodologies (transrectal or transperineal) of 14 cores or more to be used for baseline lesion localization and characterization and for follow-up, but the methodology used should be consistent at all time points for each subject. Successful lesion ablation by ExAblate would result in no residual and/or recurrent lesion at the 6 or 24 month follow-ups. Additional biopsies may be performed between 6- month follow-up visits if judged to be clinically indicated by the investigator.

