4 INVESTIGATION PLAN

4.1 Study Design

This is a multi-center, prospective, single arm study to evaluate MRgFUS treatment of intermediate risk, organ-confined prostate lesions. All subjects will be treated and then followed up clinically for up to 24 months to evaluate any procedure or device related

**Focal MR-Guided Focused Ultrasound Surgery
of Intermediate risk, Localized Prostate Lesions**

adverse events as well as to assess efficacy endpoints of the study. Additional data related to quality of life of treated subjects will also be collected.

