- 21.** Actual treatment will begin. Per each slice, planning software will compute the treatment plan with the beam path delineated. Treating physician will review/edit the sonications and make modifications as needed. Sonications will be performed according to plan.
- 22.** Effect of each sonication will be measured by MR thermometry. Acoustic power will be adjusted throughout the treatment, to achieve temperatures between 65°C and 85°C at focal point.
- 23.** Sonications will continue until entire target volume has been treated. The goal is a total procedure (i.e. ablation or sonication) time of up to 180 minutes. If the doctor determines the planned treatment is not possible after the first 3 therapeutic sonications, and another treatment session is not planned, the patient will be considered a screen failure and exited from the study. The reason for early exit will be documented on the CRF. The patient will be taken to recovery area for observation and release. The patient will undergo a 1-week follow-up visit for safety purposes, prior to study exit.
- 24.** After completion of the treatment, a final MR scan will be done. This scan will include T2 weighted and T1 contrast enhanced sequences including subtraction to evaluate tissue ablation.
- 25.** Transrectal device will be removed by physician and then patient will be transferred from the magnet/ ExAblate Suite to a recovery room for an observation period, according to clinical considerations.
- 26.** Treatment exports and all MR images taken during the study will be archived by the Sponsor.
- 27.** In the event of an incomplete treatment due to device failure, patient request, physician's decision, or unforeseen circumstance, a second treatment will be offered to the patient, provided no medical contraindications exist. Second treatment will be scheduled within 12 weeks from the original treatment. Patient follow-up visits will be based on the date of the second treatment.
- 28.** Patient should complete a post-treatment NRS.

Focal MR-Guided Focused Ultrasound Surgery of Intermediate risk, Localized Prostate Lesions

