 - d) At 6-month follow visit patients will be evaluated for physical exam with DRE and urinalysis (culture, if indicated), Multi-parametric MRI, PSA test, concomitant medications, adverse events, and completion of the ICIQ-SF, FACT-P (v4), IPSS, IIEF-15, and SF-12 questionnaires. In addition, all

Focal MR-Guided Focused Ultrasound Surgery of Intermediate risk, Localized Prostate Lesions

patients will undergo a mapping biopsy using the same technique as for screening.

- e) At 9-month follow-up visit, patients will be evaluated for physical exam, with DRE, concomitant medications, AEs and completion of the ICIQ-SF. FACT-P (v4), IPSS, IIEF-15, and SF-12 questionnaires.
- f) At 12-month follow-up visit, patients will be evaluated for physical exam, with a DRE, PSA test, clinical labs for CBC, serum chemistries, urinalysis (with culture if indicated), post-void residual and uroflowmetry if medically indicated based upon the physician's decision, concomitant medications, AEs; and completion of the ICIQ-SF. FACT-P (v4), IPSS, IIEF-15, and SF-12 questionnaires.
- g) At 18-month follow-up visit, patients will be evaluated for physical exam, with a DRE, urinalysis (with culture, if indicated) and PSA, concomitant medications, and AEs and completion of the ICIQ-SF. FACT-P (v4), IPSS, IIEF-15, and SF-12 questionnaires.
- h) At 24-month follow visit, patients will be evaluated for physical exam, with a DRE, PSA test, clinical labs for CBC, serum chemistries, urinalysis (with culture if indicated); post-void residual and uroflowmetry if medically indicated based upon the physician's decision, concomitant medications, AEs; completion of the ICIQ-SF. FACT-P (v4), IPSS, IIEF1-5, and SF-12 questionnaires In addition, all patients will undergo a mapping biopsy using the same technique as used at Baseline and 6-month follow-up.
- i) IMAGE-guided mapping biopsy between the 6-month and the 24-month visits will be done if clinically indicated, based on individual investigator medical opinion.

4.4.1 Early discontinuation of the study may occur for reasons including patient decision, investigator decision, Sponsor decision, decision to pursue alternative treatments for their tumor. Attempts should be made to complete the final visit study procedures prior to exiting the study. The reason for early discontinuation will be captured on the study Case Report Forms.

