7.3 Criteria for Removal from the Study

Early discontinuation from the study may occur for reasons including patient decision, investigator decision, Sponsor decision, protocol compliance and decision to pursue alternative treatments for their tumor. Attempts should be made to complete the final visit study procedures prior to exiting the study. The reason for early discontinuation will be captured on the study Case Report Forms.

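### A man stopped after therapeutic sonications with no further session planned is called a screen failure, and 'treated' is undefined, so the plan does not say how he counts

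*Combined protocol and SAP*

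**What the plan says.** Section 4.3 delivers energy at therapeutic power in step 20, to check the achieved dose against the predicted dose. Step 21 then states: "Actual treatment will begin". Step 22 adjusts power to reach 65-85°C at the focus, a range that section 1.1 associates with coagulation.

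Step 23 covers the case where the intended ablation "is not possible after the first 3 therapeutic sonications, and another treatment session is not planned, the patient will be considered a screen failure". The exit reason goes on the CRF, and the only follow-up it requires is this: "The patient will undergo a 1-week follow-up visit for safety purposes, prior to study exit". Step 27 separately offers a second session within 12 weeks after an incomplete treatment, including one that is incomplete by the physician's decision.

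On follow-up in general, section 2.1 says: "It should be noted that all patients will be consented and followed up all the way to 24-Months post treatment". Section 4.1 is softer: "All subjects will be treated and then followed up clinically for up to 24 months". Section 2.2 evaluates complications from the treatment day to 24 months. Section 7.3 permits early exit: "Early discontinuation from the study may occur for reasons including patient decision, investigator decision, Sponsor decision, protocol compliance". Sections 4.4.1 and 7.3 both add: "Attempts should be made to complete the final visit study procedures prior to exiting the study".

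On analysis, section 2.1.1 sets the size at 100 to 103 patients treated, while 6.2.1 gives the same range for 'subjects'. Section 6.1 limits the primary population to patients treated after site IRB approval of Amendment 4. Section 6.2.1 takes as its primary measure the proportion of treated patients with a negative biopsy, MRI confirmation of index-lesion ablation, or both, at 6 months. No section defines 'treated', names a safety or effectiveness set, or says how a man with no 6-month result is counted.

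**The concern.** A screen failure is ordinarily someone who never received the intervention. Step 23 applies the term to a man who has received therapeutic energy. By exposure he was treated; by label he was only screened. Two analysts working from this plan could build different denominators, and both could defend them.

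With no comparator and a descriptive primary analysis, the proportion and its denominator are the result. Inability to deliver the planned ablation is partly an outcome of the device and the procedure. If men are left out for that reason, the reported success describes only those in whom treatment could proceed, and the decision lies with the physician who is treating them. Some exits may be eligibility problems discovered on the table; that argues for showing them by reason, not for removing them unseen.

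There is a smaller follow-up question. Section 2.1 makes continence and potency part of the safety objective: "The risk of ExAblate treatment-related incontinence and impotence will also be assessed in this study". Step 23 itself schedules nothing after week 1.

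**Working it through.** The plan states no performance goal, power, effect size or dropout allowance, so there is no figure of its own to reproduce. The check is textual, followed by an illustration on stated assumptions.

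**1. Where 'treated' is used.** Study size (2.1.1), primary population (2.1.2 and 6.1), the count of 81 at 20 September 2018 (2.1.2 and 6.1), and the primary proportion (6.2.1). None carries a definition. It is therefore not stated whether the 81, or the 100 to 103, include step 23 exits.

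**2. When exposure starts.** Step 20 uses therapeutic power; step 21 places the start of treatment after it. Whether step 20 transmissions are among the 3 sonications in step 23 is not stated.

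**3. How far step 23 reaches.** It may mean a stop at the third sonication only, or any stop after it. On the narrow reading, no text classifies a later abandonment without a second session. On the wide reading, step 23 overlaps step 27, which covers incomplete treatment by physician's decision and is silent if no second session takes place.

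**4. What the exited man has.** Scheduled post-treatment visits are 1 week and 1, 3, 6, 9, 12, 18 and 24 months, 8 in all; step 23 requires 1 of 8. The 1-week visit includes the ICIQ-SF. The IIEF-15 is first due after treatment at month 3, and the biopsy and multi-parametric MRI at month 6.

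**5. Exposure, if step 23 is an early gate.** Section 1.4 gives 15 to 200 sonications as typical: 3/200 = 1.5% and 3/15 = 20%. On the wide reading of step 23, exposure could be greater.

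**6. Effect on the primary proportion.** Assumed: 100 completers, s successes, k exits counted as not successful. Proportion = s/(100 + k).

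| s | exits left out | k = 1 | k = 2 | k = 5 |
|---|---|---|---|---|
| 70 | 70.0% | 70/101 = 69.3% | 70/102 = 68.6% | 70/105 = 66.7% |
| 80 | 80.0% | 80/101 = 79.2% | 80/102 = 78.4% | 80/105 = 76.2% |
| 90 | 90.0% | 90/101 = 89.1% | 90/102 = 88.2% | 90/105 = 85.7% |

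The fall for one exit is 0.7, 0.8 and 0.9 point respectively. If the exits lie inside a total of 100 instead, an 80% rate in completers becomes 80% × (100 − k)/100 = 79.2%, 78.4% and 76.0%.

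Exact (Clopper-Pearson) 95% intervals: 80/100 gives 70.8-87.3%, a width of 16.5 points; 80/105 gives 66.9-84.0%. A few exits shift the estimate by less than its sampling uncertainty, but always in the same direction.

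**The case against.** The strongest reply has four parts.

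*Nothing excludes these men.* This stands. A reader might infer that the plan drops them and that its estimate is therefore biased. The documents do not say so; the bias follows only if the label is taken as an exclusion. What is established is that the plan leaves the choice open and its wording leans one way.

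*Safety is already covered.* Largely true up to exit. Section 7.1.8 puts all treatment side effects in the CRFs and the final analysis, 7.2 records device- and procedure-related events, and 7.5 has safety monitoring review all events. A reader might infer that these men's safety data are lost, or that erectile function can never be scored after exposure. Neither follows: 4.4.1 and 7.3 ask that final-visit procedures be attempted, and the 24-month visit includes the IIEF-15, the ICIQ-SF and a mapping biopsy. What remains is that step 23 mentions only the 1-week visit, and the plan does not say whether the general request also applies.

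*Early exit is allowed.* It is. Exit at 1 week is not in itself a contradiction of the 24-month follow-up, given the wording of 4.1 and 7.3.

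*It is a feasibility gate with little exposure, and any effect is assumed.* Possibly. The reach of step 23 and the role of step 20 are ambiguous, and the documents give neither an exit count nor a success rate. That limits the size of the point; it does not supply the missing denominator.

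**Conclusion.** The point holds as a gap in the analysis definitions, and should be fixed. A device-exposed man can be labelled a screen failure while the study size, primary population and primary proportion all depend on an undefined 'treated'. If the label is followed, the success proportion can only rise.

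The size is unknown. On an assumed 70-90% success rate in 100 completers, with every exit counted as not successful, it is about 0.7-0.9 point per exit. The primary analysis is descriptive and has no stated threshold, so no conclusion is shown to change. On safety the point is narrower: no assessment after week 1 is scheduled by step 23, and that has to be squared with the general request to attempt final-visit procedures.

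**What to change.** - In 6.1 and 6.2.1, define 'treated' as receipt of at least one therapeutic sonication, and state whether step 20 transmissions count.
- Put every such man in the safety set.
- In the primary proportion, count a step 23 exit with neither a 6-month biopsy nor a 6-month MRI as not successful. Show completers as a secondary analysis.
- Tabulate step 23 exits by CRF reason, so that late eligibility findings are visible, and say whether exits count toward the 100 to 103.
- Reserve 'screen failure' for men who received no therapeutic sonication.
- Reconcile step 23 with step 27, and with 2.1, 2.2, 4.4.1 and 7.3, on follow-up and on how a later abandonment without a second session is classified. The clinical rule for stopping stays with the sponsor.

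The cost is wording and one table, since the exit reason is already collected. Section 6 ties the efficacy analysis to an agreement with FDA, so the definition should be aligned with that. The downside is a slightly less favourable proportion if exits have occurred. With 81 men already treated under Amendment 4 at 20 September 2018, later follow-up may be unrecoverable for any already exited, but they can still be counted in both sets.

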4.4 Follow-up

1. Immediate post treatment follow-up and monitoring will start in the recovery room. This time period will be used to evaluate the patient's health post-treatment, and any safety related issues.
2. The Foley catheter will be removed at the end of the procedure and the patient will be re-catheterized in case of urinary retention, unless the investigator decides to keep the catheter for a longer period (e.g., due to known pre-existing urinary obstructive symptoms). In case where the urethra was included in the treatment volume, and a suprapubic catheter (SPC) is used, it may remain in the bladder until the patient is able to spontaneously urinate, with a residual post-voiding urine volume of 50 ml or less (per ultrasound imaging). Oral antibiotics will be administered as long as the SPC remains *in situ*.
3. Antibiotics may be administered based on physician's clinical judgment. Administration and cause will be captured in the CRF.
4. For this study, it is recommended that patient will be released after spontaneous urination (in case of using a Foley catheter), or according to physician's clinical decision. When using an SPC, patients should be instructed regarding handling of the catheter prior to their discharge. Catheter may be required for up to 6 weeks post-treatment.
5. Post treatment NSAID's, analgesics or alpha blockers will be administered after procedure per clinical decision and will be captured in the CRF record.
6. Follow up visits will be completed at 1-week, and 1, 3, 6, 9, 12, 18, and 24 months post-ExAblate treatment to assess adverse events and concomitant medications, as well as specific procedures outlined below:
 - a) At 1 week visit patients will be evaluated for general health (physical exam), ICIQ-SF, and NRS, concomitant medications, and AEs.
 - b) At the 1 month follow-up, patient will be evaluated by a physical exam with a DRE, concomitant medications, and AEs. Patient will be asked to complete the NRS, ICIQ-SF, and IPSS questionnaires. Proctoscopy and/or uroflowmetry will be performed in the presence of clinical symptoms, based on individual investigator judgment.
 - c) At 3 months follow-up patients will be evaluated for physical exam with a DRE, concomitant medications, AEs and completion of the ICIQ-SF, FACT-P (v4), IPSS, IIEF-15, and SF-12 questionnaires.
 - d) At 6-month follow visit patients will be evaluated for physical exam with DRE and urinalysis (culture, if indicated), Multi-parametric MRI, PSA test, concomitant medications, adverse events, and completion of the ICIQ-SF, FACT-P (v4), IPSS, IIEF-15, and SF-12 questionnaires. In addition, all

Focal MR-Guided Focused Ultrasound Surgery of Intermediate risk, Localized Prostate Lesions

patients will undergo a mapping biopsy using the same technique as for screening.

- e) At 9-month follow-up visit, patients will be evaluated for physical exam, with DRE, concomitant medications, AEs and completion of the ICIQ-SF. FACT-P (v4), IPSS, IIEF-15, and SF-12 questionnaires.
- f) At 12-month follow-up visit, patients will be evaluated for physical exam, with a DRE, PSA test, clinical labs for CBC, serum chemistries, urinalysis (with culture if indicated), post-void residual and uroflowmetry if medically indicated based upon the physician's decision, concomitant medications, AEs; and completion of the ICIQ-SF. FACT-P (v4), IPSS, IIEF-15, and SF-12 questionnaires.
- g) At 18-month follow-up visit, patients will be evaluated for physical exam, with a DRE, urinalysis (with culture, if indicated) and PSA, concomitant medications, and AEs and completion of the ICIQ-SF. FACT-P (v4), IPSS, IIEF-15, and SF-12 questionnaires.
- h) At 24-month follow visit, patients will be evaluated for physical exam, with a DRE, PSA test, clinical labs for CBC, serum chemistries, urinalysis (with culture if indicated); post-void residual and uroflowmetry if medically indicated based upon the physician's decision, concomitant medications, AEs; completion of the ICIQ-SF. FACT-P (v4), IPSS, IIEF1-5, and SF-12 questionnaires In addition, all patients will undergo a mapping biopsy using the same technique as used at Baseline and 6-month follow-up.
- i) IMAGE-guided mapping biopsy between the 6-month and the 24-month visits will be done if clinically indicated, based on individual investigator medical opinion.

4.4.1 Early discontinuation of the study may occur for reasons including patient decision, investigator decision, Sponsor decision, decision to pursue alternative treatments for their tumor. Attempts should be made to complete the final visit study procedures prior to exiting the study. The reason for early discontinuation will be captured on the study Case Report Forms.

4.4.2 Wherever possible, in cases of potential surgical resection of the gland MRgFUS-treated patients, pathology results will be evaluated and compared to the treatment and post treatment data.

5 Study Visit Schedule

See visit schedule on next pages.

**Focal MR-Guided Focused Ultrasound Surgery
of Intermediate risk, Localized Prostate Lesions**

PCa003 Study Schedule				
Visit	Window Allowance	Clinical Office and Lab Tests	Imaging **	Questionnaires
Screening	—	DRE; PSA IMAGE-guided TPBx or TRBx; Clinical labs for CBC, serum chemistries and urinalysis (cultures, if indicated); Physical Exam Concomitant medications	CT, Multi-parametric MRI (E-coil may be used)	FACT-P (v4); ICIQ-SF; IIEF-15 (SHIM); IPSS SF-12
Treatment ***	—	DRE; peripheral oxygen saturation, heart rate, and blood pressure; AEs	MR for planning, treatment and post Tx	Pre-Txt: NRS, FACT-P (v4); ICIQ-SF; IIEF-15 (SHIM); IPSS; SF-12 Post-Txt - NRS
1 week	±3 days	AEs; Physical exam; Concomitant medications		NRS; ICIQ-SF
1 month	± 7 days	AEs; Physical exam with DRE; Proctoscopy and/or post-void residual and Uroflowmetry if indicated; Concomitant medications		ICIQ-SF; IPSS NRS
3 months	± 1 week	AEs; Physical exam; DRE; Concomitant medications		FACT-P (v4); ICIQ-SF; IIEF-15 (SHIM); IPSS; SF-12;
6 months	± 1 month	AEs; Physical exam; DRE; urinalysis (culture, if indicated), PSA; TRBx or TPBx; Concomitant medications	Multi-parametric MRI	FACT-P (v4); ICIQ-SF; IIEF-15 (SHIM); IPSS; SF-12
9 months	±1 month	AEs; Physical exam; DRE; Concomitant medications		FACT-P (v4); ICIQ-SF; IIEF-15 (SHIM); IPSS ; SF-12

**Focal MR-Guided Focused Ultrasound Surgery
of Intermediate risk, Localized Prostate Lesions**

12 months	± 2 month	AEs; Physical exam; DRE; PSA Clinical labs for CBC, serum chemistries and urinalysis (cultures, if indicated); post-void residual and Uroflowmetry if indicated; Concomitant medications		FACT-P (v4); ICIQ-SF; IIEF-15 (SHIM); IPSS; SF-12
18 months	± 2 months	AEs; Physical exam; DRE, urinalysis (Culture, if indicated); PSA Concomitant medications		FACT-P (v4); ICIQ-SF; IIEF-15 (SHIM); IPSS; SF-12
24 months	± 2 months	AEs; Physical exam; DRE; PSA Clinical labs for CBC, serum chemistries and urinalysis (cultures, if indicated); post-void residual and Uroflowmetry if indicated; IMAGE-guided TRBx or TPBx; Concomitant medications		FACT-P (v4); ICIQ-SF; IIEF-15 (SHIM); IPSS ; SF-12

Focal MR-Guided Focused Ultrasound Surgery of Intermediate risk, Localized Prostate Lesions

